4.2.2.2 MI – MCMC / Reference-based imputation

MI-MCMC / Reference-based imputation will be implemented as a supportive analysis for the primary efficacy endpoint (through Week 16).

In this case, placebo will be described as the reference arm.

This procedure will use an imputation model based on data from the placebo group only (Mallinckrodt, 2013). Reference-based MI assumes that the statistical behavior of the bimekizumab and placebo-treated participants after discontinuing study medication becomes that of the placebo-treated participants. All timepoints after discontinuation of the double-blind study treatment for both the bimekizumab and placebo groups will be considered missing. Multiple imputations are used to replace missing outcomes for bimekizumab- and placebo-treated participants who discontinued using multiple draws from the posterior predictive distribution estimated from the placebo arm. For binary efficacy endpoints (eg, HiSCR₅₀ at Week 16), imputation will be done on the lesion counts before assessing the imputed results for HiSCR₅₀ response.

The steps for the procedure are as follows:

1. For non-monotone (intermittent) missing data, MCMC will be used to impute lesion count data, with Baseline antibiotic use, Hurley Stage at Baseline, and lesion count at Baseline and at each post-Baseline visit (in chronological order) being included in the imputation model. This will be done only once for each participant in order to provide a dataset with monotone missing data.
2. Data will be processed sequentially by repeatedly calling SAS® PROC MI to impute missing outcome data at visits t=1, ... T, where T is Week 16 for HiSCR₅₀.
 - a. *Initialization.* Set t=1 (Baseline visit)
 - b. *Iteration.* Set t=t+1. Create a data set combining records from bimekizumab- and placebo-treated participants with columns for covariates (Hurley Stage at Baseline and Baseline antibiotic use) and outcomes at visits 1 to t. Outcomes for all bimekizumab-treated participants are set to missing at visit t and set to observed or previously imputed values at visits 1 to t-1. Outcomes for placebo-treated participants are set to observed at visit t or observed or previously imputed values at visits 1 to t-1. The outcomes should be sorted in chronological order in the model.

- c. *Imputation.* Impute missing values for visit t using previous outcomes for visits 1 to t-1, Baseline antibiotic use, and Hurley Stage at Baseline. Note that only placebo data will be used to estimate the imputation model since no outcome is available for bimekizumab-treated participants at visit t. Consequently, the input dataset should include all study participants from placebo but only study participants from the bimekizumab arm that have values at timepoint t missing.
- d. Repeat steps 2a-2c, 100 times with different seed values (seeds ranging from 853 to 952) to create 100 imputed complete data sets. Study participants whose missing values were imputed in the last PROC MI call will be included in the input dataset for the next PROC MI call. Standard rounding rules will be applied to the imputed values. If the MI procedure yields a value outside of the pre-defined range for the given variable, the value will be updated to be within the predefined range of values for the endpoint of interest. For example, the imputed value for inflammatory nodules will be updated to 0 in the case of an imputed value less than 0.
- e. *Analysis.* For each completed data set, the outcome (response or change from Baseline) will be calculated using the complete datasets (with no missing data).

3. Each complete imputed data set will then be analyzed based on the statistical model specified in this study (logistic regression). The Week 16 results from logistic regression of each of the 100 imputed data sets will be combined for overall inference using Rubin's rules, which account for the uncertainty associated with the imputed values (Rubin, 1987). This will be done using SAS PROC MIANALYZE.

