4.2.2.1 MI – MCMC / Monotone Regression

In many cases, missing efficacy data due to study treatment discontinuation should be dependent on the observed efficacy scores, but independent of unobserved data. This would be consistent with a missing at random (MAR) pattern of missingness. To investigate the efficacy results under the assumption of data being MAR, a multiple imputation method will be applied.

Binary endpoint

For a binary endpoint (eg, HiSCR₅₀), the procedure is as follows:

1. Create a data set, one for each treatment group of participants with observed values and those needing estimation by multiple imputation. For the imputation step, a distinction is made between non-monotone missing values (ie, intermittent missing values between completed assessments) and monotone missing values (ie, where all participants data are missing after a given time point).
 - a. For the intermittent missing values, the missing values in each data set will be filled in using the MCMC method with multiple chain, monotone missing data imputing pattern, and non-informative prior for all parameters. Unless specified differently, the first 200 iterations will not be used (the “Burn-in” option). A total of 100 sets of imputations will be performed. The seed used for these imputations will be 762 and all other multiple imputation procedures described in this SAP will use this same seed as well. The resulting 100 imputed data sets will have a monotone missing pattern and will be imputed using a method for monotone missingness. Note that a separate imputation procedure must be invoked in SAS for each treatment group as the seed cannot be set for by groups beyond the first when using a by statement in PROC MI.
 - b. For monotone missing data, monotone regression will be used to impute missing data. A separate regression model is estimated for each variable with missing values (ie, measurement at each time point). Based on the resulting model, a new regression model is then drawn and is used to impute the missing values for the variable. Since the data set has a monotone missing data pattern, the process is repeated sequentially for variables with missing values. This procedure will be based on the 100 imputed datasets generated from the MCMC procedure and will be performed by imputation. The SAS® PROC MI procedure will be used for the imputation.

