1. Data after intercurrent event date (See Section 3.9) will be set to missing.
2. The same MCMC method described in Section 4.2.2.1 (Step 1a) will be implemented for non-monotone (intermittent) missing pattern values, using the same imputation model. This will be based on 100 sets of imputations.
3. Based on the 100 datasets obtained in Step 2, a monotone regression model will be applied (using the same imputation model as in Step 2) as described in Section 4.2.2.1 (Step 1b). This will be based on 1 imputation.
4. Delta adjustments will be made to imputed lesion count values at Week 16, independently in each treatment group as described below.
5. Delta adjusted imputed values will be truncated so that they are within the range of allowable values for each component.
6. Following the delta adjustments for the lesion counts, HiSCR₅₀ will then be derived based on the delta-adjusted multiply imputed data sets obtained for each component.
7. Each of the 100 imputed datasets will then be analyzed using a logistic regression model with factors of treatment group, Baseline Hurley Stage, and Baseline antibiotic use.
8. The results obtained from the 100 logistic regression analyses in Step 7 will be combined for overall inference using Rubin’s rules, and the results obtained for each shift parameter will be presented in a single table.
9. Steps 4 to 8 will be repeated so that, at each iteration, missing values are adjusted with a larger delta than at the previous iteration. The process will go on until the p-value for the odds ratio between bimekizumab and placebo is no longer statistically significant (eg, ≥ 0.025). The odds ratio, 97.5% CI (or 95% depending on the significance level being used for testing), and p-values obtained for each value of delta will be combined in one single table.

The delta adjustments result in study participants randomized to bimekizumab with missing data having a lower probability of response compared to study participants randomized to placebo with missing data. Since HiSCR₅₀ response is an endpoint for which high lesion counts are associated with a less favorable outcome:

- A positive adjustment is applied to the imputed value for study participants randomized to bimekizumab in order to increase the imputed value and decrease the likelihood of response.

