5 STUDY POPULATION CHARACTERISTICS

5.1 Study participant disposition

Summaries of reasons for screen failures (for ES), disposition of participants (for ES), disposition of analysis sets (for RS), disposition and discontinuation reasons in the Initial Treatment Period (for RS) and the Maintenance Treatment Period (for MS), as well as the participants who discontinued due to AEs in the Initial Treatment Period (for RS) and Maintenance Treatment Period (for MS) will be produced. The disposition of participants for all participants screened will include the number of participants included in each analysis set (ES, RS, SS, FAS, AMS, MS, PPS, and PK-PPS) overall and by site.

Participants are defined as completing the Initial Treatment Period if they have a Week 16 visit, or if they fail to attend the Week 16 visit but attend at least one visit in the Maintenance Treatment Period.

The following listings for participant disposition will be provided: participants who did not meet study eligibility criteria (for ES), participant disposition (for ES), participant discontinuation (RS), visit dates (for RS), participant analysis sets (for ES), participants excluded from efficacy analysis (for RS).

To assess participant disposition (entry and periods in the study) during the COVID-19 pandemic, study participant disposition will also be assessed by period of the COVID-19 pandemic (pre – during – post), by comparing the dates of visits (or events) to the dates of the COVID-19 pandemic period. The dates to categorize the periods of the COVID-19 pandemic (pre/during/post) are defined below:

- Pre-COVID-19 pandemic period: Period prior to COVID-19 pandemic start date defined as 11-Mar-2020

- COVID-19 pandemic period: Period from 11-Mar-2020 though the COVID-19 pandemic end date which is currently not defined at the time of approval of the SAP
- Post-COVID-19 pandemic period: Period after the declaration of the end of the pandemic

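### The reference-based analysis in SAP 4.2.2.2 draws intermittent lesion counts only once, so Rubin's rules miss their imputation uncertainty; the effect is probably small

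*SAP*

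**What the plan says.** SAP 4.2.2.2 describes the reference-based imputation as a supportive analysis of HiSCR50 through Week 16.

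- **Step 1** imputes intermittent lesion counts by MCMC. The model contains Baseline antibiotic use, Hurley Stage, and the counts at Baseline and at each post-Baseline visit. The step ends: "This will be done only once for each participant in order to provide a dataset with monotone missing data".
- **Steps 2a to 2c** impute the remaining monotone gaps visit by visit from a model fitted to placebo data, with Week 16 as the last visit.
- **Step 2d** reads: "Repeat steps 2a-2c, 100 times with different seed values (seeds ranging from 853 to 952) to create 100 imputed complete data sets". Step 1 is outside this loop.
- **Step 3** says the 100 logistic regressions are "combined for overall inference using Rubin's rules, which account for the uncertainty associated with the imputed values (Rubin, 1987").

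The other two procedures differ. In 4.2.2.1 step 1a, for the MCMC filling of intermittent values, "A total of 100 sets of imputations will be performed", and the monotone step then runs on each resulting data set. In 4.2.2.3 step 2 the same MCMC method is used and "This will be based on 100 sets of imputations"; step 3 adds one monotone imputation to each.

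**The concern.** Rubin's rules measure imputation uncertainty by how much the estimate varies across completed data sets. A value drawn once and copied into all 100 data sets does not vary, so it is analysed as if it had been observed. For these counts the justification given in step 3 fails, and this follows from the algorithm alone.

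Two things are at stake. The reported standard error lacks one variance component, and the estimate itself moves with the single draw. This analysis is the missing-not-at-random check that Table 8-1 and 8.2.3.2 set beside the primary result, so its interval should be built in the same way as the ones it is compared with.

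How much this matters depends on a point that step 1 leaves open. 4.2.2.1 defines intermittent gaps as "intermittent missing values between completed assessments". 5.1 counts participants as completing the Initial Treatment Period "if they fail to attend the Week 16 visit but attend at least one visit in the Maintenance Treatment Period". If visits after Week 16 enter step 1, a missing Week 16 count in such a participant is intermittent, and the endpoint itself is drawn once. If only visits through Week 16 enter, a missing Week 16 count is always monotone and is drawn 100 times. The single draw then affects only predictors.

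**Working it through.** **The plan's own figure.** The SAP states no standard error for this analysis. The nearest figure for the endpoint is the Table 2-1 power of 0.90 for HiSCR50, Q4W versus placebo (0.50 vs 0.25, 140 vs 70, two-sided 0.025).

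- Pooled proportion: (70 + 17.5)/210 = 0.4167
- SE under no difference: √[0.4167 × 0.5833 × (1/70 + 1/140)] = 0.0722
- SE under the alternative: √[0.1875/70 + 0.25/140] = 0.0668
- Power: Φ[(0.25 − 2.2414 × 0.0722)/0.0668] = Φ(1.32) = 0.907

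This agrees with the stated 0.90, and the present point does not affect it.

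**Formula.** Rubin's total variance is T = W + (1 + 1/m)B, with m = 100, W the mean within-imputation variance and B the between-imputation variance. With one shared draw of the intermittent counts, B loses the variance between draws, V. Approximately, T(one draw) = T(100 draws) − V, so the ratio of standard errors is √(1 − V/T).

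**Simulation of the procedure.** It used 140 vs 70 participants, one rounded AN-like count, and Baseline plus Weeks 2, 4, 8, 12 and 16. MCMC was run by arm for intermittent gaps, followed by placebo-only sequential regression, m = 100, and Rubin pooling of the log odds ratio. Missingness, visit schedule and correlation are assumptions.

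| Visits in step 1 | Intermittent / dropout | SE, 100 draws | SE, one draw | Ratio | SD between single draws |
|---|---|---|---|---|---|
| Through Week 16 | 5% / 10% | 0.3442 | 0.3441 | 0.9996 | 0.0117 |
| Through Week 16 | 10% / 20% | 0.3531 | 0.3519 | 0.9966 | 0.0163 |
| Through Week 16 | 20% / 20% | 0.3466 | 0.3465 | 0.9998 | 0.0220 |
| Through Week 16, rerun | 5% / 10% | 0.3321 | 0.3321 | 1.0000 | 0.0089 |
| Through Week 16, rerun | 10% / 20% | 0.3556 | 0.3551 | 0.9987 | 0.0180 |
| Later visits too | 2% / 10% | 0.3421 | 0.3402 | 0.9945 | 0.0325 |
| Later visits too | 5% / 10% | 0.3429 | 0.3379 | 0.9853 | 0.0555 |
| Later visits too, rerun | 5% / 10% | 0.3378 | 0.3345 | 0.9905 | 0.0549 |
| Later visits too | 10% / 20% | 0.3508 | 0.3435 | 0.9793 | 0.0801 |

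Each row rests on 12 simulated trials (25 for the reruns), so the third decimal is noisy.

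**Check by formula.** For later visits at 5%: √(1 − 0.0555²/0.3429²) = √(1 − 0.0262) = 0.987, against simulated 0.985 and 0.991. At 10%: √(1 − 0.0801²/0.3508²) = 0.974, against 0.979. Through Week 16, 10% / 20% rerun: √(1 − 0.0180²/0.3556²) = 0.9987, the same as simulated.

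**Dependence on the draw.** With visits through Week 16 the SD between draws is 0.009 to 0.022 against a standard error of about 0.34, or roughly 3 to 6% of it. With later visits it is 0.03 to 0.08, or roughly 9 to 24%. An SD of 0.08 on the log scale is a factor of exp(0.08) = 1.08 on the odds ratio.

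**The case against.** The strongest objection concerns size and direction.

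**Size.** The SAP favours the narrow reading. 4.2.2.2 limits the analysis to Week 16 and makes it the last imputed visit. 4.2.2.1 uses values before the time point of interest in both the MCMC and the monotone step. Placebo participants switch to bimekizumab at Week 16 (2.3.2.2), so later visits would not suit a placebo-reference model. 5.1 concerns disposition, not imputation. This stands: the 0 to 0.3% figure is the likelier one. The phrase in step 1 about each post-Baseline visit still leaves the matter open.

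**Direction.** A reader might infer that the analysis is anti-conservative and its type I error inflated. That is not shown. A simulation of singly imputed Week 16 values alone (15,000 trials, alpha 0.025) gave error rates of 2.4%, 2.6% and 3.1% at 3%, 5% and 10% missing, against 2.1 to 2.2% with repeated draws. The Monte Carlo error is √(0.025 × 0.975/15,000) = 0.13 points, so only the 10% case is clearly above nominal. That simulation also omits the placebo-based step. Imputing bimekizumab dropouts from a placebo model makes the arms positively dependent, which Rubin's variance ignores. A simulation of the whole procedure through Week 16 (one continuous score, m = 12, assumed missingness) gave reported SE 0.357 against empirical 0.333 with error rate 1.6%, and 0.364 against 0.330 with error rate 1.1%. The SE was thus 7 to 10% too large. This stands against any claim of net anti-conservatism. It does not justify dropping a variance component, because the two errors have different sources and would offset only by chance.

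**Weight.** The analysis is supportive and outside the testing sequence of 4.5. Other missing-data analyses accompany it (8.2.3.1 and 8.2.3.3 to 8.2.3.5). This also stands.

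**Conclusion.** The point holds as a minor error of method. As written, the pooled variance contains no between-imputation component for the intermittent counts, the estimate depends on one draw, and step 3's statement about Rubin's rules is wrong for those values. The SAP gives no reason for departing from the 100 draws in 4.2.2.1 and 4.2.2.3.

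Relative to 100 draws, the standard error is about 0 to 0.3% too small on the likelier reading. If later visits enter step 1, it is about 0.5 to 2% too small at 2 to 10% intermittent missingness. These figures rest on assumed missingness and correlation and on few simulated trials. The documents do not support the stronger inference that the reported p-value or interval is anti-conservative overall. The primary test, its power and the testing sequence are untouched.

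**What to change.** Reword 4.2.2.2 as follows.

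- **Step 1:** run MCMC separately by treatment group to create 100 data sets with a monotone pattern, as in 4.2.2.1 step 1a, using only visits through Week 16. Delete the sentence that limits this to one draw.
- **Step 2d:** run steps 2a to 2c once on each of these data sets, carrying data set k into replicate k, with seeds 853 to 952 as now.

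Step 3 then becomes correct as written. The same edit should reconcile the seeds, because 4.2.2.1 says all other multiple imputation procedures in the SAP use 762.

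The cost is a few lines of SAP text and a loop in the program. The estimand, the missing-data assumption being tested and the analysis model do not change.

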4.2.2.3 Tipping Point Analysis

Tipping point analyses will also be implemented as a supportive analysis for the primary efficacy endpoint.

The objective of the tipping point analyses is to evaluate the sensitivity of results to departures from the missing at random assumption and to identify the point at which departures cause results to "tip" from statistically significant to statistically non-significant. As such, these tipping point analyses will only be performed if the primary efficacy analysis results in a statistically significant treatment effect.

For tipping point analyses, data for participants after the intercurrent event date (See Section 3.9) will be changed to missing prior to imputation and, for the bimekizumab treated participants, will be changed to non-response after imputation.

The worst-case scenario will be evaluated first. All missing primary endpoint values for study participants randomized to bimekizumab (where missing values include observations after the intercurrent event date and any other missing values) will be imputed as non-responders, while all missing values for placebo-randomized study participants will be imputed as responders. While there is little justification for such an approach, it makes the most putative assumption possible against a bimekizumab treatment effect. After applying this imputation approach, a logistic regression model consistent with the one described for the primary analysis will be applied. If the p-value for the odds ratio of bimekizumab versus placebo remains significant, then no further tipping point analyses are needed.

If this analysis based on the worst-case scenario results in a p-value that is not significant (eg, greater than 0.025), then additional tipping point analyses will be performed to identify the point at which results switch or “tip” from significant to non-significant. Note that each bimekizumab dose of 320mg Q2W and 320mg Q4W will be compared to placebo independently for these analyses. If one dose regimen is tested at the 0.05 significance level as determined in Section 4.5, then the p-value in this analysis method will be 0.05 instead of 0.025 throughout for that dose. In the tipping point analysis, a shift parameter or delta adjustment is applied to missing, and subsequently imported primary endpoint values (where missing values include observations after the intercurrent event and any other missing values). These delta implemented on the primary endpoint as follows:

1. Data after intercurrent event date (See Section 3.9) will be set to missing.
2. The same MCMC method described in Section 4.2.2.1 (Step 1a) will be implemented for non-monotone (intermittent) missing pattern values, using the same imputation model. This will be based on 100 sets of imputations.
3. Based on the 100 datasets obtained in Step 2, a monotone regression model will be applied (using the same imputation model as in Step 2) as described in Section 4.2.2.1 (Step 1b). This will be based on 1 imputation.
4. Delta adjustments will be made to imputed lesion count values at Week 16, independently in each treatment group as described below.
5. Delta adjusted imputed values will be truncated so that they are within the range of allowable values for each component.
6. Following the delta adjustments for the lesion counts, HiSCR₅₀ will then be derived based on the delta-adjusted multiply imputed data sets obtained for each component.
7. Each of the 100 imputed datasets will then be analyzed using a logistic regression model with factors of treatment group, Baseline Hurley Stage, and Baseline antibiotic use.
8. The results obtained from the 100 logistic regression analyses in Step 7 will be combined for overall inference using Rubin’s rules, and the results obtained for each shift parameter will be presented in a single table.
9. Steps 4 to 8 will be repeated so that, at each iteration, missing values are adjusted with a larger delta than at the previous iteration. The process will go on until the p-value for the odds ratio between bimekizumab and placebo is no longer statistically significant (eg, ≥ 0.025). The odds ratio, 97.5% CI (or 95% depending on the significance level being used for testing), and p-values obtained for each value of delta will be combined in one single table.

The delta adjustments result in study participants randomized to bimekizumab with missing data having a lower probability of response compared to study participants randomized to placebo with missing data. Since HiSCR₅₀ response is an endpoint for which high lesion counts are associated with a less favorable outcome:

- A positive adjustment is applied to the imputed value for study participants randomized to bimekizumab in order to increase the imputed value and decrease the likelihood of response.
- A negative adjustment is applied to the imputed value for study participants randomized to placebo in order to decrease the imputed value and increase the likelihood of response.

To start, imputed values within each lesion type, will be adjusted by the same value in each treatment arm. This adjustment will be 5% of the observed range within that lesion type. Depending on the results obtained, this adjustment will be multiplied for step 9 above (2 times, 3 times the initial adjustment) until the p-value is no longer statistically significant.

Additionally, study participants randomized to bimekizumab with an intercurrent event should be set to non-response, after applying the delta adjustment outlined in Step 6 above. This ensures study participants randomized to bimekizumab do not have a higher probability of response in the tipping point analyses compared to the primary analysis (ie, a study participant randomized to bimekizumab who is non-responder in the primary analysis cannot become a responder in the tipping point analyses).

